### **Objective 3 Prospective Cohort**

From the group of donors identified as having incident and elite controller HIV infections, a smaller convenience group of willing participants will be enrolled into Objective 3 of the study. The planned study activities for Objective 3 participants are shown in Figure 3. Enrollment will take place at the time these donors attend the post-test HIV counseling visit, or, where the donors are not assessed to be ready for enrollment at that time, shortly thereafter.

Donors who agree to participate in the study will be fully consented as to the requirements of Objective 3 of the study. Donors who consent will then be enrolled on to the study and specimens collected for CD4, viral load and cytokine profiling as well as PBMC preparations. Samples will be labeled, packed and transported according to SANBS standard operating procedures which comply with all local requirements for the transportation of bio-hazardous material. All samples will be sent to the Donation Testing Laboratory in Constantia Kloof, Gauteng from where it will be sent to the appropriate laboratories for additional testing as required. Following sample collection, the participant will complete the ACASI questionnaire for Aim 1 of this study. In addition, at each follow-up visit a short questionnaire will be completed just after collection of the blood samples, using a Teleform-style form. The content of this questionnaire will assess healthcare-seeking behavior and any medicines or natural remedies the study participant has taken or initiated since the last study visit, possible side effects of these medicines and other exposures that may influence the viral dynamics of early HIV infection. Women will also be asked if they are currently pregnant.

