#### 4.2.2 Participant Enrollment

##### Modification to Current SANBS Notification Procedures:

All donors with NAT-only infections (HIV, HCV, or HBV) are contacted by letter and telephone to request return to SANBS for additional confirmation of infection. Donors are not informed of the testing results in the letter or during the phone call. Examples of standard notification letters are included (Appendix 1). Currently, all NAT yields are called back to SANBS for follow-up sample collection. SANBS staff does not discuss which virus is suspected based on the NAT yield result. Counseling is done following the testing of the additional samples. A similar letter and approach will be developed and used for persons who are determined to be recently infected based on LAg Avidity testing for HIV and anti-Hepatitis B core negative for HBV.

Currently, donors who test concordant NAT and serology positive for HBV are contacted by telephone if possible and notified of their results with a follow-up letter of the results sent by mail. During the telephone conversation as well as in the letter donors are advised to visit their doctors or local clinic.

Every effort is made to get HIV positive donors back to SANBS for MLO's to do full HIV notification and counseling. Part of this process includes referral to their doctors and/or clinics for further investigation and management. Donors are provided a letter detailing their results which they are urged to take to their doctors.

In order to support the objectives of this study, SANBS will make changes to donor notification procedures:

1. SANBS will seek to inform and counsel all early HBV infections (NAT positive, HBsAg positive or negative and anti-HBc core negative donors) using similar procedures to those used for new HIV infections.
2. SANBS will seek to inform and counsel all of the NAT yields (HIV & HBV). The standard notification letter will be changed to stress that the donor has an early or recently acquired infection. Given the range of testing that is performed on the index donation specimens we expect few notifications to be false positive notifications (See Tables 1 and 2 for standard SANBS index donation testing conducted).
3. All confirmed cases will be urged to seek medical care that conforms to South Africa national treatment guidelines for each infection.

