The purpose of objective 3 is to prospectively characterize the virology, immunology and natural history of incident HIV infection among a cohort of recently infected blood donors and a small group of elite controllers in South Africa. Because of the prospective data collection, we will use longitudinal data analysis techniques that account for the clustered nature of the data. That is, there will be multiple time points for each blood donor. Possible outcome variables will represent the time course of early HIV viremia, production of antibody, host immune response, and potential suppression of HIV infection. The predictor variables will be HIV subtype, demographic variables, predictor variables identified in objective 1a, and predictor variables identified in the HIV subtype analysis in objective 2a. These analyses for this objective will be primarily descriptive but may include proportional hazards models.

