**CURRENT MEDICAL STATUS**

B1. Since your last visit for participation in this study have you gone to your doctor or sought medical care at a clinic or hospital?

0 No **Skip to B2**

1 Yes

97 Don't Know

98 Refuse to Answer

B1a. If yes, what was the reason for seeking medical care? \_\_\_\_\_  
\_\_\_\_\_

B2. Since your last visit for participation in this study have you gone to a traditional healer?

0 No **Skip to B3**

1 Yes

97 Don't Know

98 Refuse to Answer

B2a. If yes, what was the reason for seeing the traditional healer? \_\_\_\_\_  
\_\_\_\_\_

B3. Since your last study visit have you had a cold, flu, or any other infection?

0 No **Skip to B4**

1 Yes

97 Don't Know

98 Refuse to Answer

B3a. If yes, what symptoms did you have? Please list all the symptoms you can think of such as headache, fever, body pain, chills, vomiting, diarrhea, or any other symptom that you may have had. \_\_\_\_\_  
 \_\_\_\_\_

B4. Since your last study visit have you started taking antiretroviral medicines, also known as ARVs?

- 0 No **Skip to B6**
- 1 Yes
- 97 Don't Know
- 98 Refuse to Answer

B4a. What are the names of the antiretroviral (ARV) medicines you are currently taking? \_\_\_\_\_  
 \_\_\_\_\_

To help trigger your memory, please look at the placard with pictures of medicines and then place a check mark in the box next to the medications that look like the ones you are taking:

Place ✓ if taking this medication	Medication
	AZT - Zidovudine
	ddI - Didanosine
	3TC - Lamivudine
	D4T - Stavudine
	ABC - Abacavir
	TDF - Tenofovir
	FTC - Emtricitabine
	IDV - Indinavir
	NVP - Nevirapine
	EFV - Efavirenz
	ETV - Etravirine
	ATV - Atazanavir
	LPV/r - Lopinavir/Ritonavir
	RAL - Raltegravir
	SQV - Saquinavir
	OTH - Other not pictured

B5. If yes, have you had any side effects from taking your current antiretroviral (ARV) medicines?

- 0 No
- 1 Yes
- 97 Don't Know
- 98 Refuse to Answer

B5a. If yes, what side effects did you have? Please list all the side effect you can think of, such as nausea, loss of appetite, vomiting, diarrhea, or any other symptom that you may have had. \_\_\_\_\_

B5b. Did you miss taking some or all of the doses of your current antiretroviral (ARV) medicines because of the side effects you experienced?

- 0 No
- 1 Yes
- 97 Don't Know
- 98 Refuse to Answer

B6. Are you currently taking anything else for your health such as vitamins, herbs, supplements or natural medicines?

- 0 No
- 1 Yes
- 97 Don't Know
- 98 Refuse to Answer

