3TC / AZT	Combivir	Tablet comprising 150mg 3TC and 300mg AZT	One tablet twice a day	2	See 3TC and AZT	Take with or without food
3TC / abacavir / AZT	Tyzint	Tablet comprising 150mg 3TC, 300mg abacavir and 300mg AZT	One tablet twice a day	2	See 3TC, abacavir and AZT	Take with or without food
3TC / abacavir	Kivexa (EU)	Tablet comprising 300mg 3TC and 600mg abacavir	One tablet once a day	1	See 3TC and abacavir	Take with or without food
FTC / tenofovir	Truvada	Tablet comprising 200mg FTC and 300mg tenofovir	One tablet once a day	1	See FTC and tenofovir	Take with food
NRTI / NRTI / NNRTI fixed-dose combinations						
FTC / tenofovir / efavirenz	Atripla	Tablet comprising 600mg efavirenz, 200mg FTC and 300mg tenofovir	One tablet once a day	1	See FTC, tenofovir and efavirenz	Take on an empty stomach, preferably at bedtime
FTC / rilpivirine / tenofovir	Eviplexa	Tablet comprising 200mg FTC, 25mg rilpivirine and 300mg tenofovir	One tablet once a day	1	See FTC, rilpivirine and tenofovir	Take with a meal
Non-nucleoside reverse transcriptase inhibitors (NNRTIs)						
Efavirenz	Sustiva Stocrin	600mg tablet* and 200mg capsule	600mg once a day	1 or 3	Common: Rash, dizziness, sleep disturbance, abnormal dreams, impaired concentration, nausea, vomiting, headache, tiredness, diarrhoea, anxiety, depression Rare: Psychosis, severe rash, liver problems	Take on an empty stomach, preferably at bedtime
Etravirine	Integrale	100 and 200mg* tablet	200mg twice daily	2 or 4	Common: Rash, peripheral neuropathy Rare: Severe rash (Stevens Johnson syndrome)	Take with food
Nevirapine	Viramune	200mg tablet	200mg once a day for two weeks then 200mg twice a day	2	Common: Liver toxicity, allergic reaction, rash, nausea, headache, fatigue, stomach pain, diarrhoea Rare: Severe rash (Stevens Johnson syndrome)	Take with or without food
Nevirapine	Viramune prolonged-release	400mg tablet	400mg once a day after introductory period on non-extended-release nevirapine	1	Common: Liver toxicity, allergic reaction, rash, nausea, headache, fatigue, stomach pain, diarrhoea Rare: Severe rash (Stevens Johnson syndrome)	Take with or without food

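### Objective 3 describes natural history without accounting for antiretroviral treatment, and the visit form records only new starts, so continuing treatment, stopping and adherence are lost

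*Protocol*

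**What the plan says.** Section 4.9 gives Objective 3 the aim of characterising the virology, immunology and natural history of incident HIV infection. On outcomes it says: "Possible outcome variables will represent the time course of early HIV viremia, production of antibody, host immune response, and potential suppression of HIV infection". On covariates it says: "The predictor variables will be HIV subtype, demographic variables, predictor variables identified in objective 1a, and predictor variables identified in the HIV subtype analysis" of Objective 2a. On the type of analysis it says: "These analyses for this objective will be primarily descriptive but may include proportional hazards models".

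Section 4.2.2 (Objective 3 Prospective Cohort) says that the short visit questionnaire will cover medicines and remedies that the participant has either used or begun since the previous visit, and "other exposures that may influence the viral dynamics of early HIV infection".

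The form itself, in Appendix 8, puts the question this way: "B4. Since your last study visit have you started taking antiretroviral medicines, also known as ARVs". A No goes straight to B6. That passes over B4a (ARVs currently taken), B5 and B5a (side effects) and B5b (missed doses).

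On care outside the study, section 4.2.2 (modification to notification procedures) states: "All confirmed cases will be urged to seek medical care that conforms to South Africa national treatment guidelines for each infection".

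**The concern.** ARVs lower viral load and alter the immune measures that this objective sets out to describe. The protocol foresees treatment during follow-up: it urges cases into care and asks about ARV starts at each visit. It also counts medicines among the things that can influence viral dynamics. Yet the covariate list leaves treatment out, and the protocol contains no censoring at treatment start, no restriction to untreated time and no exclusion of treated participants.

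Two things are at stake. First, if the plan is followed as written, treated and untreated visits enter the same description of the early viremic course. Section 4.5 rests the value of Objective 3 on that course: whether clade C has a prolonged early viremic phase, and how suppression proceeds. Second, the form does not deliver what section 4.2.2 promises, because it asks about starting and not about use. An analysis plan could repair the first gap, but it cannot recover answers that were never collected.

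**Working it through.** The protocol gives no figure for ARV uptake or for this bias, so there is none to reproduce. The check compares the text, counts visits, and then illustrates the size.

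**1. Could treatment enter by another route in the covariate list?** Objective 1a predictors come from comparing cases with controls. ARV use is asked only in Section L of the risk questionnaire (Appendix 7, L5 current and L6 past), which is put to Study Group 1, the HIV cases, and not to controls. It therefore cannot emerge as an Objective 1a risk factor. L5 and L6 are also asked once, at enrolment, so they cannot describe treatment begun during follow-up.

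**2. What does B4 record?** Enrolment is at about month 1 and follow-up at months 2, 3 and 6 after the index donation. Assume that all visits are attended, answers are truthful, and treatment once begun continues to month 6.

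| ARV start | Follow-up visits on ARVs | B4 = Yes | B4 = No while on ARVs |
|---|---|---|---|
| Months 1–2 | 3 | 1 | 2 |
| Months 2–3 | 2 | 1 | 1 |
| Months 3–6 | 1 | 1 | 0 |

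The share of on-treatment visits marked Yes depends on when people start, which the protocol does not give.

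- Starts spread evenly over months 1–6: mean on-treatment visits = (1/5)(3) + (1/5)(2) + (3/5)(1) = 1.6, one of them marked, so 1/1.6 = 62.5%.
- Starts split equally across the three intervals: 3 marked of 3 + 2 + 1 = 6, so 50%.

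A participant already on ARVs at enrolment can truthfully answer No at all three visits. For that person only L5 shows treatment.

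**3. What can be recovered, and what cannot?** A Yes at one visit can be carried forward, and it places the start within about one month, or within three months for the last interval. L5 and L6 cover starts before enrolment for Study Group 1. Not recoverable after the visit that records the start: whether treatment continued, when it stopped, the later regimen, later missed doses, and exact dates.

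**4. Illustrative size.** Let N = 50 (the NAT-yield target), p = share who start ARVs, and q = share of those suppressed at month 6. Assume no spontaneous suppression. Extra participants who appear suppressed = N × p × q.

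- p = 5%, q = 0.5: 50 × 0.05 × 0.5 = 1.25, about 1.
- p = 10%, q = 0.9: 50 × 0.10 × 0.9 = 4.5.
- p = 20%, q = 0.9: 50 × 0.20 × 0.9 = 9.

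Both p and q are assumptions; the documents supply neither.

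**The case against.** The strongest reply is that section 4.9 is a sketch. The outcomes are only possible ones, the work is mainly descriptive, and censoring rules or time-varying covariates are often left to a statistical analysis plan, which is not shown here. The sponsor collects medicine data and is plainly aware of the issue. This stands in part: no sentence says that treated and untreated visits will be pooled. But the protocol does state a covariate list, and treatment is not on it. A descriptive mean trajectory that mixes the two kinds of visit is biased as a natural-history estimate without any formal model. The form's wording is outside the reach of an analysis plan.

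A reader might infer that the form makes any later correction impossible. The documents do not support that. A recorded start can be carried forward, the enrolment interview adds baseline status, and censoring at ARV start is feasible with the data as planned.

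A reader might also infer that treated incident participants would be counted as elite controllers. Section 4.5 links suppression to that small group and defines it by NAT-negative, antibody-positive status, whereas the incident group is NAT-positive and antibody-negative. Under those definitions, drug suppression does not move a participant between groups. Section 4.9 does not repeat the link, however, and the incident viremia course is affected either way.

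Finally, the B4a tick list does not match the Appendix 9 placard. Thirteen pictured products, such as "FTC / tenofovir / efavirenz", have no box of their own, and the last row reads "OTH - Other not pictured". This does not add to the bias. B4a has a free-text line for drug names, several combinations can be ticked by component, and a missing box does not change whether a start is recorded.

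**Conclusion.** The point holds in a limited form. As written, Objective 3 describes natural history with no provision for antiretroviral treatment. The visit form, contrary to its stated purpose, cannot distinguish a continuing user from an untreated participant on the answers from that visit alone. ARV starts can be bracketed; continuation, stopping, later regimen, adherence and exact dates cannot.

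The size is not known. In the illustration it runs from about 1 to about 9 extra apparently suppressed participants among 50, depending wholly on assumed uptake and assumed suppression on treatment. A reader might work out a fixed fall in mean viral load by placing every treated participant at the assay floor of 40 copies/mL. The documents do not support such a figure: they give no untreated mean and no uptake, and no reason to think that every treated participant reaches the floor by month 6 whenever treatment began.

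The defect does not undermine the objective, but it should be corrected because part of the loss is permanent once visits have taken place.

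**What to change.** 1. In section 4.9, Objective 3, add that natural-history trajectories are censored at first reported ARV use (from B4, or from L5/L6 at enrolment), that a sensitivity analysis keeps all visits with time-varying ARV status, and that suppression while on ARVs is not counted as spontaneous control.
2. In Appendix 8, reword B4 to ask at every visit about current ARV use and any use since the last visit, with start and stop dates. B4a to B5b are then completed whenever the answer is yes.
3. Optional tidy-up, separate from the bias: relabel the last row of the B4a list as Other.

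The cost is a short addition to the analysis section and one revised question on the visit form. Section 4.6 says that all interview instruments need OMB approval, so the revised wording would have to be covered by that clearance. The statistical price is fewer late natural-history visits after censoring. Nothing in participants' care changes.

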#### **4.10. Human Participants**

**Procedures & risks:** The participant will complete a self-administered computer based questionnaire on HIV and/or HBV risk behaviors. There is risk of lost confidentiality regarding HIV and HBV status and risk behaviors, minor risk of discomfort and bruising related to phlebotomy, and a risk of psychological stress due to disclosure of drug resistance results for participants in Objective 1a. Similarly, for the Objective 3 prospective study there may be minor risk of psychological stress from providing longitudinal CD4 and HIV viral load testing results.

**Recruitment, consent and protection against risks:** Recruitment will occur during the initial notification visit, and or at the final notification visit. Participants will be given the opportunity to complete the study procedures including the risk factor interview at another time. The study will be conducted in accordance with approval of IRB's at both UCSF and SANBS. All measures will be implemented to protect privacy and confidentiality including using participant ID

numbers instead of names on all study questionnaires and blood sample labels, maintaining a secure database, limiting the number of research staff with access to patient identifiers needed for contact.

**Potential benefits to participants:** If the results of these tests for drug resistance in Objective 1a indicate a participant has an HIV infection resistant to medications, these results will be provided to participant, and clinically important for the participant to be able to obtain appropriate medical care. Recently infected participants in the Objective 3 prospective study may benefit from the provision of free CD4 and HIV viral load testing.

**Importance of knowledge to be gained:** Significant benefit to public health in South Africa relating to better understanding of the epidemiology of incident HIV and incident HBV infections, and to SANBS in terms of knowledge applicable at the recruitment of safer blood donors.

**Women and minorities:** Within the South African context the majority population is Black and one of the minority populations is White. Enrollment of controls will be stratified to cases on the basis of race (population group). This is necessary for the scientific design of the study because HIV prevalence and incidence is significantly higher in the Black population and socioeconomic and behavioural factors differ significantly between the White and Black populations in South Africa. In order to obtain an accurate assessment of behavioural risks, we have decided that stratified matching on race is essential. Nevertheless, we expect overall enrollment into the study for both cases and controls to contain a much higher percentage of Black and population groups other than White when compared to the SANBS donor population, because of projected HIV and HBV infection rates. No restrictions based on gender will be used, we also expect women to be represented in the recent infection cases at or above their proportion in the donor base due to higher incidence of HIV in women compared to men in South Africa. For HBV we are unsure of whether women will be over-represented as cases.

**Children:** Children under the age of 18 will not be enrolled.

#### **4.10.1 Data Security**

Data in this study will be kept confidential, and US investigators and members of the DCC will not have access to personally identifiable information (PII). At the SANBS study sites, key study personnel will have access to records with PII. For example, written signed consent forms. Study documents with PII will be stored in secure locations separate from study data (eg. laboratory results and questionnaires). Identifying information from donors that is temporarily linkable to the laboratory results, routine donation records and our study specific-questionnaires for the

purpose of proper identification and notification of each donor will only be available to SANBS operational staff. We will take several steps to minimize the possibility of inadvertent disclosure of the identity and information of participants. First, data are tracked and linked with a donation identification number (DIN) created at the time a person donates at SANBS. In addition a donor number is created to track individuals longitudinally. For this study, none of the datasets transferred to the US will contain PII, rather the DIN and an assigned study participant identification number will be used to link the donation history, health and risk screening data, laboratory results and study specific questionnaires entered into the study database.

Limitations on who can access donor information already exist within SANBS. Only those individuals with job responsibilities that require access to PII have access to donor names and contact information. Such access is controlled through computer systems that only allow working on password protected workstations that require individual usernames and passwords. Similar restrictions on access will be in place for the study research staff.

Due to the sensitive nature of the study, the following steps are to be taken to protect the personal information of individuals recruited and/or enrolled in the study. The goal of this security plan is to put in place procedures that will reduce the risk of release of personal or sensitive information related to the study participants. The below items are the key points to achieve data security and participant privacy during the study period.

- Require the use of a two-factor authentication process to access the study management system (SMS).
- Store study materials in access-controlled rooms (use of key or access card to gain entry)
- Use computers with access-level control for SMS, including:
  - Individual level username and password requirements for all staff with access to study computers
  - Separately store files with PII. These data files reside on local systems that will be backed up on a regular weekly schedule.
  - Impose a mandatory screen saver requiring re-login to the SMS after 5-minutes of inactivity
  - Study-specific usernames assigned to staff
- Instruct staff to lock all study computers when they leave rooms
- Open the study files only when needed.
- If printing is required, print reports and other materials with identifying information on local printers in access-controlled spaces/rooms
- SANBS staff working on the REDS-III study will sign a non-disclosure agreement as part of their training and certification on this HIV/HBV protocol.

